9.5. Analysis of Laboratory and Biomarker Endpoints

9.5.1. Albuminuria

Change from Baseline in the urinary albumin:creatinine ratio stratified by albuminuria category at baseline (normoalbuminuria, microalbuminuria and macroalbuminuria), will be compared between ertugliflozin and placebo-treated subjects. In addition, albuminuria progression, defined as a change from normoalbuminuria to either microalbuminuria or macroalbuminuria or from microalbuminuria to macroalbuminuria, will be assessed comparing the baseline data to the data collected according to the following definitions:

- Normoalbuminuria: <30 mg/g (albumin:creatinine ratio).
- Microalbuminuria: ≥30mg/g to ≤300 mg/g (albumin:creatinine ratio).
- Macroalbuminuria: >300 mg/g (albumin:creatinine ratio).

Regression of albuminuria will be defined as subjects noted to have an improvement in albuminuria defined as moving from macroalbuminuria to microalbuminuria (or normoalbuminuria) or from microalbuminuria to normoalbuminuria.

9.6. Safety Analysis

The safety analysis population will consist of all randomized and treated subjects, ie, all randomized subjects who received at least one dose of investigational product in this trial.

The Medical Dictionary for Regulatory Activities (MedDRA) will be used to classify all AEs with respect to system organ class and preferred term. Summaries of AEs will include treatment-emergent AEs according to treatment group.

Two approaches will be used for handling safety data occurring after the initiation of glycemic rescue therapy. The first approach will exclude all data following the initiation of rescue, in order to avoid the confounding influence of the rescue therapy. The second

approach will include data following the initiation of rescue therapy. For the overall study analyses, the “including rescue” approach will be considered primary for all safety endpoints as, after Week 18, subjects are treated to standard of care, and there is no longer glycemic rescue. For glycemic sub-study analyses, the “including rescue” approach will be considered primary for analyses of SAEs and discontinuations of study drug due to AEs, and the “excluding rescue” approach will be considered primary for all other endpoints. Descriptive statistics will be used to summarize results and changes from Baseline in clinical laboratory tests, vital signs, and ECGs.

Furthermore, a 3-tier approach will be used to summarize AEs. Tier-1 consists of AEs of special clinical interest and will include AEs or collections of AEs related to urinary tract infection, genital mycotic infection, symptomatic hypoglycemia and hypovolemia. Where available, standard MedDRA queries may be used to pool different AE terms that are related to the Tier-1 AEs. The precise AE terms that will contribute to the Tier-1 endpoints will be determined prior to unblinding. For these events, the percentage of subjects with incident AE, the risk difference, its 95% confidence interval, and p-value will be provided. The confidence intervals and p-values are not adjusted for multiplicity and therefore must be considered accordingly. Tier-2 AEs are those that are not Tier-1, but that occur in a pre-specified minimum number of subjects in any treatment arm. For the overall study, this requirement will be at least 0.5% of subjects in any treatment arm, and for each sub-study, the requirement will be at least 4 subjects in any treatment arm. The cut-off of at least 4 events was chosen because the 95% confidence interval for the between-group difference in percent incidence will always include zero when treatment groups of equal size each have less than 4 events and so adds little to the interpretation of potentially meaningful differences. For these events, the percentage of subjects with incident AE, the risk difference and its 95% confidence interval will be provided. Tier-3 AEs are all other AEs (neither Tier-1 nor Tier-2). For Tier-3 AEs, only within-group incidence proportions will be tabulated.

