6.6. Discontinuation of Investigational Product

All efforts should be made to follow randomized subjects for the entire duration of the study. Discontinuation of investigational product does not imply or constitute withdrawal of the subject from the study.

Subjects who temporarily or permanently discontinue treatment with investigational product, should remain in the study and continue to be followed for collection of information on cardiovascular events, other events eligible for adjudication, and SAEs. Investigators should try to obtain the most complete collection of data as possible, weighing the subject’s willingness to participate with the scientific integrity of the protocol. The protocol offers subjects the option of continuing in the study off investigational product by: (1) attending the normally scheduled clinic visits; (2) attending the annual clinic visits only; (3) receiving phone contacts to collect information on cardiovascular events/SAEs, without attending clinical visits. The site phone contacts could occur either at the time of the normally scheduled visits or they could occur just annually and/or at the completion of the trial. The sole exception to this requirement is when a subject fully withdraws consent for both continued treatment with investigational product and study procedures (see Section 6.7).

Subjects who have not withdrawn consent, but who have discontinued from investigational product may initiate any other therapy as needed (previously prohibited medications may be used). Permanent discontinuation of investigational product must be registered in IVRS.

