8. ADVERSE EVENT REPORTING

8.1. Assessing and Recording Adverse Events

An adverse event is defined as any untoward medical occurrence in a patient or clinical investigation subject administered a pharmaceutical product and which does not necessarily have to have a causal relationship with this treatment. An adverse event can therefore be any unfavourable and unintended sign (including an abnormal laboratory finding, for example), symptom, or disease temporally associated with the use of a medicinal product or protocol-specified procedure, whether or not considered related to the medicinal product or protocol-specified procedure. Any worsening (ie, any clinically significant adverse change in frequency and/or intensity) of a preexisting condition that is temporally associated with the use of the sponsor's product, is also an adverse event.

Changes resulting from normal growth and development that do not vary significantly in frequency or severity from expected levels are not to be considered adverse events. Examples of this may include, but are not limited to, teething, typical crying in infants and children and onset of menses or menopause occurring at a physiologically appropriate time.

Sponsor's product includes any pharmaceutical product, biological product, device, diagnostic agent or protocol-specified procedure, whether investigational (including placebo or active comparator medication) or marketed, manufactured by, licensed by, provided by or distributed by the sponsor for human use.

Adverse events may occur in clinical trials, or as prescribed in clinical practice, from overdose (whether accidental or intentional), from abuse and from withdrawal.

For randomized subjects only, all adverse events that occur after the consent form is signed but before randomization must be reported by the investigator if they are the result of a protocol specified intervention, including but not limited to washout or discontinuation of usual therapy, diet, placebo treatment or a procedure. From the time of randomization through 14 days following cessation of treatment, all adverse events must be reported by the investigator. Such events will be recorded at each examination on the Adverse Event case report forms/worksheets. The reporting timeframe for adverse events meeting any serious criteria is described in section Serious Adverse Events. The investigator will make every attempt to follow all subjects with non-serious adverse events for outcome.

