8.4. Immediate Reporting of Adverse Events to the Sponsor

8.4.1. Serious Adverse Events

A serious adverse event is any adverse event occurring at any dose or during any use of sponsor's product that:

- Results in death;
- Is life threatening;
- Results in persistent or significant disability/incapacity;
- Results in or prolongs an existing inpatient hospitalization;
- Is a congenital anomaly/birth defect;
- Is a cancer;
- Is associated with an overdose;
- Is another important medical event.

Refer to [Table 5](#) for additional details regarding each of the above criteria.

For the time period beginning when the consent form is signed until randomization, any serious adverse event, or follow up to a serious adverse event, including death due to any cause, that occurs to any subject must be reported within 24 hours to the Sponsor if it causes the subject to be excluded from the trial, or is the result of a protocol specified intervention, including but not limited to washout or discontinuation of usual therapy, diet, placebo treatment or a procedure.

For the time period beginning at randomization through 14 days following cessation of treatment, any serious adverse event, or follow up to a serious adverse event, including death due to any cause, whether or not related to the Sponsor's product, must be reported within 24 hours to the Sponsor either by electronic media or paper. Sponsor Contact information can be found in the Investigator Trial File Binder (or equivalent).

Additionally, any serious adverse event, considered by an investigator who is a qualified physician to be related to the sponsor's product that is brought to the attention of the investigator at any time outside of the time period specified in the previous paragraph also must be reported immediately to the sponsor.

All subjects with serious adverse events must be followed up for outcome.

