With two enrollment periods of 19 months each and assuming an event rate of 3.5% per annum for MACE, a total of approximately 8000 subjects (about 4000 per enrollment cohort) randomized in a 1:1:1 ratio to ertugliflozin 5 mg, ertugliflozin 15 mg or placebo will be sufficient to accrue approximately 714 MACE events within approximately 5.0 years and approximately 939 MACE events within approximately 6.1 years from the start of this study. These calculations assume that subjects will withdraw from the study at a rate of 5% per annum.

Power for Secondary Hypotheses

For the Stage 2 analyses of secondary endpoints, using an O'Brien-Fleming alpha-spending approach and assuming accrual of at least 442 and 582 composite events of cardiovascular death or hospitalization for heart failure at the interim and final analysis respectively, the study will have approximately 90% power to demonstrate superiority of ertugliflozin to placebo on the composite of cardiovascular death or hospitalization for heart failure when the true HR=0.75. Moreover, assuming accrual of at least 287 and 377 cardiovascular death

events at the interim and final analysis respectively, the study will have approximately 83% power to demonstrate superiority of ertugliflozin to placebo on cardiovascular death when the true HR=0.725. With accrual of at least 144 and 190 renal composite events at the interim and final analysis respectively, the study will have approximately 79% power to demonstrate superiority of ertugliflozin to placebo on the renal composite endpoint when the true HR=0.65.

9.1.1. Sample Size for Insulin with or without Metformin Add-on Glycemic Sub-Study:

The sub-study is powered to demonstrate superiority of ertugliflozin compared with placebo in reducing HbA1c from Baseline to Week 18. It is estimated that a minimum of 450 subjects will be enrolled into the sub-study. The sub-study enrollment will not be allowed to exceed 50% of the overall trial sample size. The final determination of inclusion in the sub-study will be based on a programmatic assessment of the sub-study criteria.

In two recent studies of another SGLT2 inhibitor (dapagliflozin) in subjects with type 2 diabetes receiving high doses of insulin, estimates of the standard deviation of the change from baseline in HbA1c after 24 weeks ranged up to a maximum of 0.98%.^{15,16} Therefore, a standard deviation of 1.0% was taken as a conservative estimate for sample size calculations.

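### Section 9.6 compares Tier-1 and Tier-2 adverse events only as crude percentages over years of unequal time on drug, and states no exposure-adjusted measure

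*Protocol*

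**What the plan says.** Protocol section 9.6 sorts AEs into three tiers.

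- **Tier-1** (urinary tract infection, genital mycotic infection, symptomatic hypoglycemia, hypovolemia): "For these events, the percentage of subjects with incident AE, the risk difference, its 95% confidence interval, and p-value will be provided".
- **Tier-2** (other AEs reaching 0.5% of subjects in any arm of the overall study): "For these events, the percentage of subjects with incident AE, the risk difference and its 95% confidence interval will be provided".
- **Tier-3**: within-group proportions only.

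The safety population is "all randomized subjects who received at least one dose of investigational product in this trial". On scope, section 9.6 says: "Summaries of AEs will include treatment-emergent AEs according to treatment group". Its only caveat on the p-values is that they are not adjusted for multiplicity.

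Section 8.1 sets the observation window: "From the time of randomization through 14 days following cessation of treatment, all adverse events must be reported by the investigator". Section 9.1 sets the duration, with the final analysis at "approximately 939 MACE events within approximately 6.1 years from the start of this study" and two 19-month enrollment periods.

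For serious AEs the text is not consistent. Section 6.6 says that subjects off drug "should remain in the study and continue to be followed for collection of information on cardiovascular events, other events eligible for adjudication, and SAEs", and section 3.1 agrees. Section 8.4.1 sets the general reporting period as "For the time period beginning at randomization through 14 days following cessation of treatment, any serious adverse event", and outside it requires only events judged related to the product.

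**The concern.** A crude percentage depends on how long each subject is observed. Here observation of non-serious AEs ends shortly after drug is stopped, so the arm that stays on drug longer collects more AEs at the same hazard. Randomization does not protect against this, because stopping happens afterwards.

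The documents describe mechanisms that could pull either way. After Week 18 background therapy may be intensified freely (section 5.5.1), and needing a prohibited agent, including another SGLT2 inhibitor, means stopping study drug (sections 4.2 and 6.7.4); this might affect placebo more. Section 1.2.2 describes genital infection, urinary infection and volume depletion as class risks; these might prompt stopping on ertugliflozin, and they correspond to three of the four Tier-1 groups.

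At stake is whether a Tier-1 difference can be read as a drug effect. More stopping on placebo can produce a false signal. More stopping on ertugliflozin can hide a real one.

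**Working it through.** **1. The plan's own follow-up.** Inputs from section 9.1: 4,000 subjects per cohort, 19 months of enrollment each, MACE rate λ = 0.035 and withdrawal w = 0.05 per year. Expected events are the sum over cohorts of 4,000 × mean[λ/(λ+w) × (1 − exp(−(λ+w)t))], with uniform enrollment. The start of Cohort 2 is not given. Taking 2.5 years after study start gives 716 events at 5.0 years and 946 at 6.1 years, against 714 and 939 stated. Mean study follow-up is then about 3.6 years.

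**2. Crude AE percentage with no drug effect.** For AE hazard h and stopping rate d:

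P = mean over t of h/(h+d) × (1 − exp(−(h+d)t))

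- Cohort 1: t uniform on 4.5 to 6.1 years (6.1 − 19/12 = 4.5).
- Cohort 2: t uniform on 2.2 to 3.8 years (start near 2.3 years).
- The 14-day tail is ignored.
- About 8,000 subjects at 1:1:1 gives about 2,667 per arm, or 5,333 with doses pooled.
- **Assumed, not in the documents:** h and d. Ertugliflozin stopping is set at 7% per year.

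Worked case, h = 0.04, placebo stopping 9% per year:

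- Placebo: 15.3% (Cohort 1) and 9.9% (Cohort 2), average 12.60%.
- Ertugliflozin: 16.0% and 10.2%, average 13.11%.
- Spurious difference: +0.52 points.
- One dose vs placebo: SE = √(0.1260×0.8740/2667 + 0.1311×0.8689/2667) = 0.92 points; z = 0.52/0.92 = 0.56; rejection = P(Z > 1.96 − 0.56) + P(Z < −1.96 − 0.56) = 8.7%.
- Pooled: SE 0.79 points, rejection 10.0%.

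| AE hazard per 100 subject-years | Placebo stopping per year | Spurious difference (points) | Rejection, one dose | Rejection, pooled |
|---|---|---|---|---|
| any | 7% | 0.00 | 5.0% | 5.0% |
| 2 | 8% | +0.14 | 5.5% | 5.6% |
| 4 | 9% | +0.52 | 8.7% | 10.0% |
| 4 | 10% | +0.76 | 13.3% | 16.3% |
| 6 | 10% | +1.08 | 17.5% | 21.9% |

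Moving Cohort 2 to 2.0 to 3.6 years, which fits step 1 better, changes the last row to +1.05 points, 16.9% and 21.1%.

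**3. Masking.** True hazard ratio 1.25, placebo hazard 3 per 100, placebo stopping 7% per year. When ertugliflozin stopping rises from 7% to 10% per year, the risk difference falls from 2.32 to 1.60 points. Power falls from 88% to 59% pooled, and from 77% to 47% for one dose.

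**4. Where it matters little.** With a hazard of 10% per year for six months and 1% thereafter, 10% vs 7% stopping gives about +0.23 points and about 6.5% rejection (pooled). Over 18 weeks the shift is about 0.01 points and rejection stays at 5.0%.

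**5. Person-time rates.** Events per subject-year to last dose + 14 days recover the truth in every constant-hazard case run, for example 5.00 vs 5.00 per 100 where the crude percentages were 15.3% and 16.2%.

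**The case against.** Several objections stand and limit the point.

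- **A reader might infer that no exposure-adjusted AE analysis is planned anywhere.** The documents cannot show that. Section 9 says its methods are further detailed in a statistical analysis plan that may modify them, and the SAP supplied is a heart-failure supplement, not the primary SAP.
- **A reader might infer that the comparisons are biased.** That depends on unequal stopping. The only related figure is 5% per year study withdrawal, not split by arm, and it is not a drug-stopping rate. In the worked case the spurious difference is smaller than its standard error.
- **A reader might take the pooled range as the main one.** Sections 9.1 and 9.2 pool doses for the cardiovascular analyses; section 9.6 refers to treatment groups and arms and states no pooling.
- **A reader might infer that all AE observation ends at 14 days.** Sections 3.1 and 6.6 continue SAE and adjudicated-event collection off drug, and section 8.4.1 keeps late related SAEs reportable. The premise is clear only for non-serious AEs.
- **Decision weight is modest.** Tier-1 p-values are nominal and control no hypothesis or stopping rule; cardiovascular endpoints and the renal composite already use Cox models. A crude on-treatment percentage is a valid description. The difficulty lies in reading its difference and p-value as risk at equal exposure.

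None of this supplies an exposure-adjusted measure in section 9.6.

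**Conclusion.** The point holds against section 9.6 as written, for the overall study, and mainly for non-serious AEs that accrue over time. With unequal stopping, the crude risk differences and Tier-1 p-values mix drug effect with time on drug, in a direction that cannot be known in advance. On the assumed rates (constant hazard 2 to 6 per 100 subject-years, placebo stopping 8 to 10% against 7% per year) the nominal 5% test rejects about 5.5 to 17.5% of the time per dose and about 6 to 22% pooled. These figures illustrate sensitivity; they do not estimate what happened in this trial. The cardiovascular conclusions are untouched. It is an inexpensive improvement that should be made.

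**What to change.** For the overall study, amend section 9.6, or confirm that the primary SAP already does the following:

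1. For Tier-1 and Tier-2 AEs, add first events per 100 subject-years at risk, counted to last dose + 14 days, with the rate difference and 95% CI. For Tier-1, a Cox hazard ratio for time to first event, stratified by Cohort, is an alternative.
2. Base the Tier-1 between-arm inference on that measure and keep crude percentages as descriptive columns.
3. Report time on drug by arm.
4. Reconcile sections 3.1 and 6.6 with section 8.4.1 on SAE collection after discontinuation, so that the at-risk period for SAEs is defined.

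The sub-studies need no change. The cost is wording and programming: AE start dates are recorded (Table 5), permanent discontinuation is registered in IVRS (section 6.6), and last-dose windows of 14, 30 and 365 days are already used for cardiovascular endpoints (SAP Appendix 2).

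There are two downsides. Rates assume a constant hazard, which the Cox version avoids. Both options censor soon after drug stops, which may be informative when AEs themselves cause stopping; item 3 helps the reader judge that.

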6.1.1. Dispense Hypoglycemia Assessment Log and Instruct on Hypoglycemia Symptoms and Management

At Day 1 visit (V2), the site will review the symptoms and management of hypoglycemia with the subject. The site will counsel the subject to perform a fingerstick glucose measurement if any symptoms occur that may be related to hypoglycemia (eg, weakness, dizziness, shakiness, increased sweating, palpitations, or confusion), but also to avoid delay in treating these symptoms.

The subject will be instructed to complete the Hypoglycemia Assessment Log for any symptomatic episode he or she believes may represent hypoglycemia. If a fingerstick glucose has been obtained before or shortly (ie, within a few minutes) after treatment, the value should be recorded in the log. In addition, subjects will be instructed to record in the log any fingerstick glucose values ≤ 70 mg/dL (3.9 mmol/L) regardless of the presence of clinical symptoms.

Subjects should be instructed to contact the investigational site to report:

- Any episode of hypoglycemia for which assistance was required (ie, severe hypoglycemia);
- Any episode of fingerstick glucose ≤ 70 mg/dL (3.9 mmol/L) with or without symptoms.

Note: As indicated, subjects will record symptoms and/or fingerstick glucose measurements that they believe are related to hypoglycemia in the log. Each episode should be evaluated by the investigator and recorded on the Hypoglycemia Assessment (HA) eCRF. For episodes determined to be hypoglycemia (symptomatic or asymptomatic), and for all glucose values ≤ 70 mg/dL (3.9 mmol/L), regardless of whether they are considered an adverse event, the HA eCRF must also be completed. Each event of symptomatic hypoglycemia must be reported as an adverse event on the adverse event eCRF. Each episode of asymptomatic

hypoglycemia considered by the investigator to be an adverse event should also be reported on the adverse event eCRF.

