7.6.2. Management of Hypoglycemia

Subjects will be instructed to check fingerstick glucose when they have symptoms consistent with hypoglycemia such as hunger, headache, dizziness, light headedness, sweating, palpitations, tachycardia, tremulousness, irritability, blurred vision, and disorientation. Subjects should be instructed to call the site should these symptoms occur and/or worsen before next visit, see [Section 6.1.1](#).

Any episode of hypoglycemia must be captured on the HA eCRF. For definition of hypoglycemic episode and severity categorization, refer to [Section 7.6.3](#) below.

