Assuming a standard deviation of 1.0% and a lost to follow up rate of 10%, a sample size of 450 subjects (150 per arm) will provide approximately 98% power to detect a difference of 0.5% in the reduction of HbA1c from Baseline to Week 18 between ertugliflozin and placebo using a 2-sided 0.05 alpha level test.

9.1.2. Sample Size for SU Monotherapy Add-on Glycemic Sub-Study:

The primary endpoint for the sub-study is the HbA1c change from Baseline to Week 18. It is estimated that approximately 170 subjects will be enrolled into the sub-study. The final determination of inclusion in the sub-study will be based on a programmatic assessment of the sub-study criteria.

Assuming a standard deviation of 1.0%, a lost to follow up rate of 10%, and a sample size of 170 subjects (~56 per arm), the power to detect a between treatment difference of 0.6% will be approximately 85% using a 2-sided alpha level of 0.05.

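### In the supplied documents symptomatic hypoglycaemia is compared only by share of subjects affected, so recorded repeat episodes enter no planned comparison; the cost in power depends on rates the documents do not give

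*Protocol*

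**What the plan says.** Protocol section 9.6 lists symptomatic hypoglycaemia among the Tier-1 events. For these, "the percentage of subjects with incident AE, the risk difference, its 95% confidence interval, and p-value will be provided". The same paragraph adds that "The confidence intervals and p-values are not adjusted for multiplicity".

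Collection is by episode. Section 6.1.1 states "Each episode should be evaluated by the investigator and recorded on the Hypoglycemia Assessment (HA) eCRF" and "Each event of symptomatic hypoglycemia must be reported as an adverse event on the adverse event eCRF". Section 7.6.2 repeats the rule: "Any episode of hypoglycemia must be captured on the HA eCRF". Section 7.6.3 has each event classified by severity and type.

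Neither supplied document plans a count, rate or recurrent-event analysis of hypoglycaemia. Both plan such analyses elsewhere: Protocol section 9.3 uses Andersen-Gill models for recurrent cardiovascular events, and SAP section 3 does so for heart failure hospitalisation. The opening of Protocol section 9 leaves detail to a statistical analysis plan. The supplied SAP describes itself as a heart-failure supplement to a primary SAP, which was not available.

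**The concern.** Under the planned comparison a subject with one episode and a subject with twenty count the same. Safety and tolerability is a primary objective of all three glycaemic sub-studies (Protocol sections 2.2.1, 2.3.1 and 2.4.1). All of them enrol subjects on insulin or a sulfonylurea, and their arms are small: about 150, 56 and 86 subjects (sections 9.1.1 to 9.1.3). At that size the choice of summary can decide whether an increase in episodes is visible.

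SAP section 3 gives the same reason for looking beyond first events in heart failure: an analysis of first events leaves out all that follow. The reasoning carries over to hypoglycaemia, where the follow-on data are already on the case report form.

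**Working it through.** **1. Check the sample sizes on the plan's own figures.** For the insulin sub-study the protocol says "Assuming a standard deviation of 1.0% and a lost to follow up rate of 10" per cent, "a sample size of 450 subjects (150 per arm) will provide approximately 98% power to detect a difference of 0.5" percentage points, "using a 2-sided 0.05 alpha level test". With n = 150 × 0.9 = 135 per arm:

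power = Φ(δ / (σ√(2/n)) − 1.96) = Φ(0.5 / √(2/135) − 1.96) = Φ(4.11 − 1.96) = 98.4% (stated 98%).

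The same formula with δ = 0.6 gives 85.4% for SU monotherapy (n = 50.4; stated 85%) and 96.2% for metformin with SU (n = 77.4; stated 96%). Arm sizes and alpha are therefore read correctly.

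**2. Inputs for hypoglycaemia.** The documents state no incidence, episode rate, dispersion, target effect or power. All of the following are assumptions: negative binomial episode counts with placebo mean μ and dispersion k, a constant rate ratio R, equal follow-up, two-sided 0.05, and 150 per arm with no loss.

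- Share with any event: p = 1 − (1 + kμ)^(−1/k)
- Planned test: z = (p₁ − p₀) / √(p₀(1 − p₀)/n + p₁(1 − p₁)/n)
- Rate test: z = ln R / √((1/μ₀ + k)/n + (1/μ₁ + k)/n)
- Power = Φ(z − 1.96)

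**3. One case in full:** μ₀ = 0.8, k = 3, R = 1.5, so μ₁ = 1.2.

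- Shares: p₀ = 1 − 3.4^(−1/3) = 0.335 and p₁ = 1 − 4.6^(−1/3) = 0.399.
- Planned test: z = 0.0637 / 0.0555 = 1.15, power Φ(−0.81) = 21%.
- Rate test: standard error √((4.25 + 3.833)/150) = 0.232, z = 0.4055 / 0.232 = 1.75, power Φ(−0.21) = 42%.

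The drug adds 0.4 episodes per subject but only 0.064 newly affected subjects. About 84% of the added episodes are therefore repeats that the planned test cannot count.

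**4. Range over incidence** (150 per arm, R = 1.5, k = 2; differences taken before rounding):

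| Placebo share with event | μ₀ | Planned test | Rate test | Loss (points) |
|---|---|---|---|---|
| 5% | 0.05 | 12.5% | 13.2% | 0.7 |
| 10% | 0.12 | 18.6% | 21.3% | 2.7 |
| 20% | 0.28 | 25.7% | 35.1% | 9.3 |
| 30% | 0.52 | 28.1% | 45.6% | 17.5 |
| 40% | 0.89 | 27.5% | 53.5% | 26.1 |

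At a 20% share the loss is 7 to 11 points for k = 1 to 4. At 5% to 10% it is 0 to 4 points. At a placebo mean of 0.2 episodes with k = 1, 3 or 6 (shares of 12% to 17%) it is 5 to 6 points.

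**5. Other settings** (k = 1 to 4, shares 5% to 40%):

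- Sub-studies, R = 1.25: 0 to 9 points.
- SU monotherapy (56 per arm), R = 1.5: 0 to 11 points. Both tests are weak there.
- Overall study (about 2,667 per arm, from 8,000 randomised 1:1:1), R = 1.5 or 2.0: 0 to 4 points for one dose and 0 to 1 for pooled doses, because both tests are already near full power.
- Overall study, smaller effects: at R = 1.25 the pooled loss is 0 to 6 points for k = 1 to 2 and 6 to 30 for k = 4.

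**6. A different mechanism.** Suppose the drug changes only who is affected. By simulation at 150 per arm, raising the share from 20% to 32% gives the planned test 66% power and the rate test 39% to 46%. Raising it from 40% to 56% gives about 80% against 40% to 51%. Over the cases run, the planned test is better by about 20 to 40 points.

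**The case against.** The strongest reply is that this is a choice, not an error. Tiered percentages with risk differences are coherent, no safety endpoint is powered, and the Tier-1 p-values are openly unadjusted. That stands, and it limits the point to a supportive addition.

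Three stronger readings are tempting, and the documents support none of them.

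- A reader might infer that the plan always costs 10 points of power or more. Steps 4 to 6 show that this depends on incidence, dispersion, effect size and mechanism, none of which is stated.
- A reader might infer that repeat episodes are never compared anywhere. That can be said only of the supplied documents, since the primary SAP was not available.
- A reader might infer that repeat episodes are the likely form of a drug effect. No section says so, and Protocol section 1.2.1 reports no increase in hypoglycaemia risk in Phase 2. At low incidence most added episodes are in newly affected subjects: with k = 2, R = 1.5 and a 5% placebo share, 0.0224 / 0.0270 = 83%. The planned test counts those.

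A further objection concerns the rate model. Protocol section 5.5.1 lets background therapy be reduced or stopped after clinically significant hypoglycaemia, so a first episode can lower the risk of later ones, perhaps more often in the arm with more hypoglycaemia. This stands as a caution. In a simulation of the step 3 case with each subject's rate cut by 50% or 75% after the first episode in both arms, the rate test's power fell from 43% to 38% and 32%, against about 21% for the planned test. Type I error stayed near 5%. The gain shrinks but persists. After Week 18 background therapy may be changed freely, which makes an overall-study rate comparison less clean still.

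**Conclusion.** The point holds in a conditional form. In the supplied documents, repeat episodes of symptomatic hypoglycaemia are recorded but enter no between-arm comparison.

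In the insulin sub-study this gives up roughly 10 points of power or more if about 20% or more of placebo subjects have an event and the episode rate rises about 1.5-fold. At the same ratio the loss is about 0 to 6 points at the lower shares examined (about 5% to 17%). It is mostly under 10 points at rate ratio 1.25 in the sub-studies and usually negligible in the overall study at 1.5 or more. If the drug changes only who is affected, the planned test is the better one.

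These figures rest on assumed negative binomial counts, a constant rate ratio and equal follow-up. Because neither test is better throughout, the result argues for having both. It does not justify replacing or demoting the risk difference. This is a minor, inexpensive improvement, not a defect in the planned test.

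**What to change.** In Protocol section 9.6 and the primary SAP, keep the Tier-1 percentage, risk difference, 95% confidence interval and p-value for symptomatic hypoglycaemia unchanged. Beside them add a supportive episode-rate analysis:

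- negative binomial regression of episodes per subject, or a rate model with robust variance, with log at-risk time as offset;
- the same including-rescue and excluding-rescue rules as the incidence analysis;
- rate ratio and 95% confidence interval for each dose against placebo, first for the three 18-week sub-studies.

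The cost is a few lines of text and one extra model per comparison, with no new data, visits or subjects. Three downsides should be stated. A few subjects with many episodes can influence the rate ratio. One more unadjusted comparison is added. Background-therapy reductions after hypoglycaemia can dilute the rate difference, so the result should be read together with the incidence result. If the primary SAP already contains such an analysis, a cross-reference from section 9.6 is enough.
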